2.7. Endpoints

The primary endpoint is the proportion of patients who are not able to complete treatment due to excessive toxicity. Toxicity will be tabulated by type, frequency, and severity of AEs and serious AEs (SAEs), laboratory abnormalities, and other safety findings.

The secondary endpoints are:

- Percentage of patients achieving a point in time objective response (either complete or partial response [CR or PR]) after 2 cycles of infigratinib. Tumor mapping will be performed from the endoscopic evaluation (after any biopsies) and this will be used to compare to pathologic (NUX/Ux cohort) or ureteroscopic (endoscopy cohort) findings in order to determine responses.
- Tumor mapping will be performed based on endoscopic findings, noting location, number of tumors, tumor architecture, and location of biopsies; and will again be performed during pathologic evaluation again noting size, location, number of tumors, architecture, and absence of tumor at any previously identified tumor. A difference of 3mm will be considered within error of measurement.
- Mutational analysis will be performed on FFPE tumor tissue using a comprehensive mutation panel (T200.2) which we have used in prior studies and includes all previously identified UTUC mutations, including all relevant FGFR3 alterations including hot spots, copy number variations and fusions. Blood collected at baseline will be used as germline source.
- All analyses will be performed on patients stratified as having or not having FGFR3 alterations. Descriptive statistics will be used to summarize various clinical parameters.
- The same methods will also be used to explore the association of AEs such as hyperphosphatemia with response.
- Percentage of patients with no evidence of disease 12 months after surgery

- Changes in patient reported QOL outcomes will be measured using a validated questionnaire (EORTC QLQ-C30 v3), administered at 3 time points: 1. enrollment (after enrollment and before first dose), 2. after completion of 2 cycles and prior to surgery, and 3. at 1 month postoperative check.

The exploratory endpoints are:

Tumor Studies:

- Single cell (sc)RNAseq will be performed on fresh frozen tumors using 10x Genomics platform. Tumor cell heterogeneity, FGFR3 gene expression, and tumor microenvironment will be profiled. All bioinformatics data analysis will be performed in the MD Anderson Genomics core as part of the Rare Tumor Initiative Program (2014-0938)
- Multiplex immunohistochemistry will be performed using FFPE tissue (biopsy and final pathologic specimen) and undergo interrogation for immunologic studies by the MD Anderson Rare Tumor Initiative Program. For patients with a complete response without residual tumor, the bed of the largest pretreatment tumor (based on tumor map) will be used for immune studies.
- Tissue prioritization: Given the potentially limited biopsy samples, use of biopsy and pathologic tumor tissue will be prioritized in the following order and sources: 1. Mutational analysis (FFPE), 2. RNAseq (fresh frozen), 3. TMA (FFPE).

Biomarkers:

Voided urine will be collected preferentially but will be substituted with selective upper tract washings when voided urine is not available or insufficient. Urine and blood will be collected at 3 time points (pretreatment/enrollment, after completion of infigratinib treatment/preoperatively, and 30 days postoperatively). Urine processing follows established standard operating procedures. Samples are stored at -80°C and then sent to Fox Chase Cancer Center for further analyses ([name] laboratory, with whom we have an existent collaboration and MTA). DNA is isolated from the urine sample and DNA is checked for quality, typically yielding several micrograms of high molecular weight DNA. DNA is also isolated from PBMC prior to initiation of therapy to use as a germline reference sample. DNA from germline and pre/post-treatment/post-op time points are subjected next generation sequencing using the HaloPlexHS platform with a targeted depth of 1000X covering 54 well characterized cancer genes. These genes are enriched in patients with urothelial carcinoma (including FGFR3). HaloPlexHS uses pre-amplification single molecule tags to filter taq errors occurring during PCR, thus greatly enhancing the power to detect rare alleles. In preliminary experiments, our approach was validated to be highly sensitive and accurate, detecting >60% of tumor tissue mutations in the urine and identifying additional mutations in the urine that are not seen in tissue.

Urine will be characterized for FGFR3 hotspots or other missense variants and we will track their variant allele frequency in longitudinal samples. Presence of point mutations in the pre-treatment urine will be correlated with pathological response as an a priori predictive biomarker. Separately, we will also correlate clearance of all pre-treatment

mutations after treatment with infiratinib and after surgery with pathologic response as a post hoc biomarker. Correlation will be determined using Fishers exact test for both analyses.

Cell-free DNA (cfDNA):

To explore the association of cfDNA with response, we will collect blood at pretreatment/enrollment, post-treatment/preoperatively, and 30 days postoperatively (30mL each time point). These samples will be processed and stored until tumor studies are completed and results available. Of all patients identified as having tumor FGFR3 alterations, 5 will be randomly selected to have their baseline cfDNA assayed; if 3 or more are found to have detectable FGFR3 alterations, then up to 5 more patient baseline samples will be run. Those found to have detectable baseline FGFR3 alterations in their cfDNA will have their second time point assayed. These results will be correlated to disease burden, pathologic findings, disease grade, stage, objective response, and immune correlates. For cfDNA we will leverage the availability of a 70-Gene Liquid Biopsy Panel (LBP-70). The validated next generation sequencing (NGS)-based panel will be run in the MD Anderson Department of Pathology and Laboratory Medicine. Peripheral blood is collected into Streck tubes designed to reduce admixture of circulating cfDNA with cellular DNA from blood cells during transport. The NGS-based panel is designed to detect single nucleotide variants (SNVs) and small insertion-deletions (Indels) in all 70 genes included in the panel. In addition, amplifications (copy number variants; CNVs) and fusions (translocations) involving selected genes can also be detected. Specifically in regard to this study, the panel is able to detect mutations/indels, amplifications, and fusions of FGFR3. The comprehensive liquid biopsy test utilizes molecular barcode technology and sophisticated error detection algorithms to allow a sensitive and accurate detection of low level mutations.

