8.2.7. Ophthalmic Assessments

Ophthalmologic examination will be performed by an ophthalmologist, or optometrist who is supervised by an ophthalmologist, at the times indicated in [Section 1](#). These assessments will include visual acuity testing, slit lamp examination of the anterior eye segment, intraocular pressure, and fundoscopy. Additional examinations such as specular microscopy (that enables a magnified, direct view of the corneal epithelium), corneal pachymetry, retinal optical coherence tomography (OCT), and dilated fundoscopy will be performed as clinically indicated.

9. STATISTICAL PLAN:

The primary objective is to evaluate the safety and tolerability of infigratinib as neoadjuvant therapy. Up to 20 patients will be enrolled in the study. The study will estimate proportion of patients who are not able to complete treatment (discontinuation) due to excessive toxicity along with the 90% exact confidence interval (NOTE: excessive toxicity is defined as treatment related adverse events that cause patients not to complete 2-cycles of planned treatment schedule). Toxicities will be tabulated using frequency and percentage by grade and their relations to treatment. Assuming a 30% of discontinuation due to excessive toxicity, the 90% confidence interval would be (13.1%, 46.9%) with a sample size of 20. Toxicity data will be summarized for the whole group of patients and for patients with eGFR \geq 50 and eGFR 30-49 separately. The safety analysis included all patients who received at least one dose of infigratinib.

Toxicity monitoring:

The study will monitor the incidence of not completing treatment or delay >14 days of surgery due to excessive toxicity using this monitoring rule. That is stop the trial early if $\text{Prob}(\text{Ptox} > 0.3 | \text{data}) > 0.85$. Where Ptox denotes the proportion of patients not being able to complete treatment or delay >14 days of surgery. The corresponding stopping boundaries are that the trial will be stopped early if at any time it is observed that $(n \text{ of patients not completing treatment or delay } >14 \text{ days of surgery due to excessive toxicity} / N \text{ of patients treated}) \geq 3/5, 4/(6-8), 5/(9-10), 6/(11-13), 7/(14-16), \text{ and } 8/(17-19)$. This stopping rule will be applied for each cohort of eGFR \geq 50 and eGFR 30-49 separately. If one cohort stops early due to excessive toxicity, the other will continue accruing as per protocol criteria and toxicity monitoring rule.

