Descriptive statistics will be used to summarize quantifications as continuous variables and frequency and percentage along with 90% CI will be used to summarize categorical variables. Wilcoxon rank sum test and Fisher's exact test will be used to explore the association between objective response and secondary outcomes, e.g. cfDNA, expression of markers, FGFR3 alteration type. The same methods will also be used to explore the association of AEs such as hyperphosphatemia with response. Recurrence at 12 months will be summarized using proportion and 90% confidence interval as a binary outcome, and also be estimated using the Kaplan-Meier method as a time to event variable. The association between time to event variables and markers will be explored using log rank test and univariable Cox model. With the small sample size, the analysis will probably only descriptive. The analysis will be performed in all patients and by FGFR3 alteration status if applicable. For data collected using the EORTC QLQ-C30 questionnaire, we calculate raw score (RS) and linear transformed score (Score) for each of the five functional scales, three symptom scales, a global health status / QoL scale, and six single items at each time point [Reference: Fayers PM, Aaronson NK, Bjordal K, Groenvold M, Curran D, Bottomley A, on behalf of the EORTC Quality of Life Group. The EORTC QLQ-C30 Scoring Manual (3rd Edition). Published by: European Organisation for Research and Treatment of Cancer, Brussels 2001]. For each of these scales, paired t test or Wilcoxon signed rank test will be used to evaluate the changes of the Scores between two time points. Linear mixed models will also be fitted to evaluate the changes in Scores over time.

9.1.1.1. Adverse Events: Safety analyses will be performed for all subjects who receive at least one dose of study drug according to the treatment they receive.

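### Urine variant allele frequency is tracked over time, but the only planned on-treatment urine comparison with pathologic response is yes/no clearance of all baseline mutations by Fisher's exact test; a comparison of the change in allele frequency should be added

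*Combined protocol and SAP*

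**What the plan says.** Section 2.7 (Endpoints, Biomarkers), repeated in Appendix 4 (Urinary biomarkers), collects urine before treatment, before surgery and 30 days after surgery. It is sequenced at a "targeted depth of 1000X covering 54 well characterized cancer genes". For FGFR3 hotspots and other missense variants the plan states that "we will track their variant allele frequency in longitudinal samples".

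Two analyses follow. The first uses baseline urine: "Presence of point mutations in the pre-treatment urine will be correlated with pathological response as an a priori predictive biomarker". The second uses later samples. It begins "Separately, we will also correlate clearance of all pre-treatment" and continues "mutations after treatment with infiratinib and after surgery with pathologic response as a post hoc biomarker". The test is then fixed: "Correlation will be determined using Fishers exact test for both analyses".

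Section 9 (Statistical Plan) adds a general rule: "Wilcoxon rank sum test and Fisher's exact test will be used to explore the association between objective response and secondary outcomes". Its examples are cfDNA, marker expression and FGFR3 alteration type. It also provides for descriptive summaries of continuous quantities and expects the small sample to make the analysis mainly descriptive. On size: "Up to 20 patients will be enrolled in the study".

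The documents do not give a read threshold that defines clearance, a rule for patients with no baseline urine mutation, or a comparison of VAF change with pathologic response.

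**The concern.** A quantitative before-and-after measurement is planned, but the comparison with response uses it only as cleared or not cleared. A patient whose VAF falls tenfold and one whose VAF does not move count the same if both remain detectable. In a trial this small, that can hide a real association.

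The yes/no variable also carries two features unrelated to drug effect. A patient with several baseline mutations must lose all of them, while a patient with one need lose only one. And a variant near the detection limit can be missed on re-sampling although nothing has changed. The plan does not ask for baseline mutation count or VAF to be shown beside clearance, so a reader could not see either effect.

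At stake is the reading of an exploratory marker that may be carried into, or dropped from, the later studies this trial is meant to inform. No primary, secondary or safety conclusion depends on it.

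**Working it through.** The plan gives no power, alpha or effect size for the urine analyses, so there is no figure to reproduce. From the documents: at most 20 patients, 1000X depth, 54 genes. Everything else below is assumed.

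**1. Information lost by the yes/no cut.** For a normally distributed change cut so that a fraction f counts as cleared, large-sample efficiency relative to Wilcoxon is φ(c)² / [f(1−f)] ÷ (3/π), where c is the normal quantile of f and 3/π = 0.955.

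| Fraction cleared | φ(c) | φ(c)²/[f(1−f)] | Relative to Wilcoxon | Loss |
|---|---|---|---|---|
| 10% | 0.175 | 0.342 | 0.358 | 64% |
| 20% | 0.280 | 0.490 | 0.513 | 49% |
| 30% | 0.348 | 0.576 | 0.603 | 40% |
| 50% | 0.399 | 0.637 | 0.667 | 33% |

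**2. How coarse Fisher's test is here.** With 4 responders and 8 non-responders, 3/4 against 0/8 cleared gives p = 0.018. One cleared non-responder (3/4 against 1/8) gives 0.067, and 4/4 against 2/8 gives 0.061. With 10 and 10, 6/10 against 1/10 gives 0.057.

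**3. Power, two-sided 5%.** Assumed: 4 against 8 patients; baseline VAF log-uniform from 0.5% to 20%; Poisson reads at depth 1000; a variant called at 3 or more reads; SD of log10 change 0.5 between patients and 0.2 between mutations. Mean falls in responders and non-responders are 1.0 and 0.2 log10 (10-fold and 1.6-fold), or 1.5 and 0.3 log10 (32-fold and 2-fold). Ranges cover repeated runs.

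| Mean log10 falls | Mutations per patient | Fisher on clearance | Wilcoxon on log VAF change |
|---|---|---|---|
| 1.0 and 0.2 | 1 | 0.09–0.12 | 0.44–0.48 |
| 1.0 and 0.2 | 1–4 | 0.03–0.05 | 0.52–0.53 |
| 1.5 and 0.3 | 1 | 0.26–0.29 | 0.73–0.78 |
| 1.5 and 0.3 | 1–4 | 0.21–0.22 | 0.82–0.84 |

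With no difference between groups, Fisher rejects in 0.000–0.002 of runs and Wilcoxon in about 0.05. With a 2.5 log10 fall in responders, Fisher reaches about 0.60–0.83 and Wilcoxon 0.88–0.99.

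A different model with all 20 patients, half of them responders, and a mean of 5 mutations gives Fisher 0.01 / 0.15 / 0.58 against Wilcoxon 0.72 / 0.97 / 1.00, for extra natural-log falls of 2 / 3 / 4 in responders.

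**4. Dependence on baseline mutation count.** If each mutation clears independently with probability 0.7, all k clear with probability 0.7^k: 0.70 for one and 0.7⁵ = 0.17 for five. Independence is too harsh, because changes within a patient are likely to be correlated. Under the step 3 model with a mean fall of 1.5 log10, all-clear is about 70% with one mutation. With five it is about 33% if baseline VAFs differ independently, and 50% if they are shared. If all mutations clear strictly as a block, the dependence vanishes.

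**5. Chance dropout at unchanged VAF.** At VAF 0.5% the expected reads are 1000 × 0.005 = 5, and P(2 or fewer) = e⁻⁵(1 + 5 + 12.5) = 0.125. At 0.3% the mean is 3, and P = e⁻³(1 + 3 + 4.5) = 0.423. Averaged over the 0.5% to 20% range it is only about 0.8%, so this matters for variants near the limit and not in general.

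**The case against.** The strongest reply has four parts.

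- **Clearance is the sponsor's stated hypothesis.** Appendix 4 cites preliminary data tying urinary mutation clearance after neoadjuvant chemotherapy to pathologic complete response, and says its wider use is untested. This stands: replacing or demoting clearance would be a reviewer's preference. It does not argue against adding VAF change, since those data concern another therapy and complete response only.
- **Section 9 already covers continuous markers.** A reader might infer from this concern that VAF goes wholly unanalysed. The documents do not support that: VAF is tracked, and Section 9 provides descriptive summaries of continuous quantities. But its Wilcoxon sentence concerns objective response and does not name urine VAF, while the urine-specific text names Fisher alone. The gap is the missing comparison of VAF change with pathologic response.
- **The power figures depend on the assumptions.** This stands. The direction was the same in every non-null setting tried, but Fisher does well when falls are very large, and the cut loses little if response is truly a threshold effect. The 4-and-8 split is also assumed. The figure of over 60% in Section 2.7 is the share of tissue mutations found in urine, so it does not give the number of patients with a detectable mutation.
- **VAF change has its own difficulties.** Undetected variants need a floor value, and upper tract washings may replace voided urine, which could shift VAF between visits. Both stand as small costs.

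**Conclusion.** The concern holds as a low-priority improvement. The one on-treatment urine comparison with pathologic response uses a yes/no result, most naturally read as all-or-none although the text does not spell this out. A more informative measurement is collected and not compared with response.

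The loss is substantial. A reader might go further and say that most of the information is lost, but that holds only when fewer than about 20% of patients clear. Nor can it be said that Fisher's test has little chance in general; that applies to the 10- to 32-fold falls assumed in the first simulation. The dependence on mutation count is real but moderate once within-patient correlation is allowed for. A reader might also infer that patients without a baseline mutation would be scored as cleared; the documents are silent on this.

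Fisher's test for the other urine analysis, presence of a baseline mutation, is not at issue. The endpoint is exploratory and expected to be mainly descriptive, which limits the consequence.

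**What to change.** In Section 2.7 and Appendix 4:

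- Keep the pre-specified clearance analysis by Fisher's test, and state the read threshold that defines clearance.
- Add the per-patient change in log VAF from the pre-treatment to the pre-operative sample, compared between responders and non-responders by the Wilcoxon rank sum test already named in Section 9.
- Define one summary in the same way for everyone, for example the mean over baseline variants, with FGFR3 VAF as a supplementary display. Using FGFR3 in some patients and a panel mean in others would tie the measure to FGFR3 status, which is itself studied as a correlate of response.
- Report clearance beside the number and VAF of each patient's baseline mutations.
- Limit both on-treatment analyses to patients with at least one baseline urine mutation, and show the others separately.
- Set the floor value for undetected variants in advance, and record whether each sample was voided urine or a washing.

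The cost is a few lines of wording and one further analysis on data already to be produced. It should be settled before urine results are compared with response, so that the added analysis is not a post hoc choice.

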3. INVESTIGATIONAL PLAN

3.1. Overall Study and Correlative Design

[figure not shown]

Figure 1: Study Design. Top row shows the clinical design, bottom row the correlative data and tissue collected.

4. STUDY POPULATION

4.1. Inclusion Criteria

1. Low grade UTUC, or high grade UTUC and not eligible for cis-platin neoadjuvant chemotherapy either due to medical comorbidities (eg, cardiac dysfunction, hearing loss, GFR<50), or based on <49% risk prediction of non-organ confined disease by clinical nomogram (PetrosF et al Urol Oncol 2019 Apr;37(4):292).
2. Undergoing: A) Nephroureterectomy or ureterectomy, or B) ureteroscopic management
3. Have adequate pre-treatment biopsy tissue available for mutational analysis, as determined by the study pathologist, prior to enrollment. Any biopsy of index UTUC tissue available within 8 weeks of enrollment may be used. Patients with recurrent low grade UTUC can have tissue used within 12 weeks of enrollment at the PIs discretion.
4. Calculated or measured creatinine clearance ≥ 30 mL/min.
5. Have an Eastern Cooperative Oncology Group (ECOG) performance status ≤ 2 .
6. Are able to read and/or understand the details of the study and provide written evidence of informed consent as approved by IRB/IEC.
7. Have recovered from AEs of previous systemic anti-cancer therapies to baseline or Grade 1, except for alopecia.
8. Are able to swallow and retain oral medication.
9. Are willing and able to comply with scheduled visits, treatment plan and laboratory tests.
10. If a woman of childbearing potential (WOCBP), must have a negative pregnancy test within 7 days of the first dose of study drug. A woman is not of childbearing potential if she has undergone surgical sterilization (total hysterectomy, or bilateral tubal ligation or bilateral oophorectomy at least 6 weeks before taking study drug) or if she is post-menopausal and has had no menstrual bleeding of any kind including menstrual period, irregular bleeding, spotting, etc., for at least 12 months, with an appropriate clinical profile, and there is no other cause of amenorrhea (e.g., hormonal therapy, prior chemotherapy).

WOCBP and males whose sexual partners are WOCBP must agree to use barrier contraception and a second form of highly effective contraception ([Clinical Trials Facilitation Group, 2014](#)) while receiving study drug and for 3 months following their last dose of study drug. Alternatively, total abstinence is also considered a highly effective contraception method when this is in line with the preferred and usual lifestyle of the subject. Periodic abstinence (e.g., calendar, ovulation, symptothermal, post-ovulation methods) and withdrawal are not acceptable methods of contraception.

Sexually active males must use a condom during intercourse while taking drug and for 3 months after the last dose of the study drug and should not father a child during this period. A condom is required to be used also by vasectomized men as well as

during intercourse with a male partner to prevent delivery of the drug via seminal fluid.

